  - Relationship-building empathetic telephone calls between lay caller and participant. Calls provide an opportunity for participants to discuss whatever they wish to share, and provide support for participants' goals for exercise, nutrition, sleep and medication adherence. In the course of engagement, if the caller feels like the participant can benefit from checking in with their regular clinic provider, they may suggest doing so. In addition, if a participant mentions a social need (such as transportation, food, housing), the caller may suggest some potential social resources for the participant to call. In addition, if the caller feels the participant could benefit from a pre-selected list of YouTube videos, that includes people talking about their life with diabetes, the caller may decide to share it with them. Calls occur 3X a week in first month and 1X a week in subsequent months for 6 months. Participants have agency in informing some aspects of how frequently they're called. After the first week they can adjust calls to a maximum of 5X a week or down to 2X a week (minimum of 2X/week for the first month). After the fourth week all calls shift to weekly. After the 8th week they can adjust calls to 2X every 4 weeks or stay on weekly schedule. Calls average 10 minutes per call or less. The participant may also receive communication via text message about their upcoming phone calls.
  - A letter sent twice in 6 months (Phase 1) to all participants in a callers panel of participants that reflect learnings from participants themselves. No identifiable information will be in these letters.
  - Automated Monthly text messages during months 7-12 (the follow-up phase) with pre-filled customized communications prepared by their caller as simple reminders of tips they discussed during the first 6 months.

**Control:** Participants in the control arm receive –

- Material aspects of elements from the Intervention arm:
- Diabetes management information for people with low literacy (print) at the start of phase 2 (after the 6 month assessment).
- Small health-promoting incentive:

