- Choice of a health-promoting tool offered as one of the final questions of the 6 month assessment. A choice will be provided at the end of the 6 month surveys between a pedometer and a smart weigh scale of equivalent value. If neither of these options are applicable based on health or other limitations, back-up options will be offered to them (fitness resistant bands or exercise program for upper body fitness). The tool will be mailed within the 7th month.
- A choice 2 items from the same set of items used for the Intervention arm in Phase 1 related to healthier living, each <\$25/-. This will be offered as one of the final questions of the 6 month assessment. The selected items will be mailed out to the participant in the 8th month and 10th month.
- Participants in the control arm do not receive the communications elements, telephone calls or letters, and otherwise continue with their normal standard of care.
- Participants in the control arm do not receive any text messaging reminders related to the program. To prevent loss to follow-up in the control arm, we will send research study reminder text messages about upcoming measurement appointments.

**Measures:** Primary outcome is Hemoglobin A1C at 6 months (repeated measures at 3 and 6, 9 and 12 months). The measurements will be taken at Lone Star clinic sites, Dell Medical School at The University of Texas at Austin, or other community-based sites, by a member of the research team. Secondary outcomes include Blood pressure through direct measurement and self-reported depression (PHQ-9), anxiety (GAD-7), general mental and physical health (SF-12) and self-reported healthcare utilization and will also be measured at Lone Star clinic sites, Dell Medical School at The University of Texas at Austin, or other community-based sites, by a member of the research team. In addition, process measures include measurements directly from the telephone call system: calls placed/attempted; calls connected (someone spoke); call duration. See below for table of all measures and method of collection.

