**Measure Collection:** Biomedical measures will be directly collected in person at their clinic site, Dell Medical School at The University of Texas at Austin, or a community site that is convenient (A1C and Blood pressure). Patient-reported measures will be collected through self-report on a tablet (or paper copy if participant chooses) at the same time biomedical measures are collected. Electronic Health Record measures will be collected via a data agreement with Lone Star Circle of Care (LSCC).

Measure	Freq	ΤοοΙ	
Program Effects			
Hemoglobin A1C	Baseline/3 mths/6 mths/9 mths/12mths	Finger stick on portable device	

Blood Pressure	Baseline/3 mths/6 mths/9 mths/12mths	Automatic blood pressure cuff
Depression	Baseline/3 mths/6 mths/9mths/12 mths	PHQ-9
Anxiety	Baseline/3 mths/6 mths/9 mths/12 mths	GAD-7
General Health	Baseline/3 mths/6 mths/9 mths/12 mths	SF-12
Healthcare Utilization (PCP & BH clinic, Hosp, ED visits)	Baseline/3 mths/6 mths/9 mths/12 mths	Customized (4 new questions added)
Healthcare Utilization (PCP visits, BH visits)	Data pulls for data collected during program	LSCC ElecHealthRecord
Medication Related to DM and HTN	Baseline/3 mths/6 mths/9 mths/12mths	Customized
Medication Adherence Survey	Baseline/3 mths/6 mths/9 mths12 mths	Med Adherence Report Scale (MARS 5)
Diabetes Self-Management	Baseline/3 mths/6 mths/9 mths/12 mths	Perceived Diabetes Self- Management Scale (PDSMS)
Diabetes Self Care	Baseline/3 mths/6 mths/9 mths/12 mths	Summary of Diabetes Self-Care Activities (SDSCA)
Diabetes Self Efficacy	Baseline/3 mths/6 mths/9 mths/12 mths	Stanford Self-Efficacy for Diabetes Scale
Diabetes Distress	Baseline/3 mths/6 mths/9 mths/12 mths	Diabetes Distress Screening Scale
Loneliness	Baseline/3 mths/6 mths/9 mths/12 mths	UCLA 3-item Loneliness Scale
Onset Date of Diabetes	Baseline	Customized
Social Needs Survey	Baseline/6 mths/12 mths	Adapted from PRAPARE
Social Support	Baseline	Lubben Social Network scale
Participant Demographics	Baseline	Customized
Household demographics	Baseline	Customized
Interest in Calling Others	6 mths	Customized
Program Satisfaction	6 mths (intervention arm only)	Customized
Program Improvement	12 mths (intervention arm only)	Customized
Program Implementation		
Call Occurrence	Continuous (daily; did it happen)	Twilio report
Call Connection	Continuous (daily; did the call connect to a person)	Twilio report
Call Duration	Continuous (daily); for every call placed, duration	Twilio report

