We will test differences in the trajectory of A1c over the course of six-months with three assessments (baseline, 3- and 6-months) for those who receive empathy calls to support diabetes self-management versus those who do not receive these support calls. We will rely on linear mixed effect regressions with random terms to model individual differences in both the intercept and change terms, accounting for the clustering effect of shared lightly trained callers. We will predict these trajectories using the following person-level covariates: grouping indicator, terms to capture diabetic treatment type and dose, change in PHQ9 from baseline to 6-month depression. The cross-level interaction of grouping indicator with time will constitute the effect of interest. In addition, if change in depression predicts the person-specific slopes for A1c and does so more strongly for those in the intervention than control group, we would have evidence that depression management affects A1c course. Similar models will be constructed for the secondary outcome of depression, PHQ9 across three waves of data collection, with frequency/duration of support calls across those waves modeled as a time-varying covariate. Person-level covariates will include grouping indicator, terms to capture change in A1c from baseline to 6-months. If change in A1c predicts person-specific slopes for depression and does so more strongly for those in the intervention than control, we would have preliminary evidence that improved control of A1c affects course of depression, an unlikely outcome. The outcome of these mixed effect regressions will permit a preliminary estimate of the mediational role of depression on A1c management in phase-I. We will estimate those indirect effects using bootstrapped standard errors using the MPlus modeling framework for longitudinal change from baseline to 6-months. Healthcare utilization outcomes both self-reported and obtained from LSCC will be harmonized into a composite score of utilization. Depending on the distribution of each aspect of utilization (ER visits, hospitalization, PCP visits), we will construct models to predict differences between the intervention and control arm while covarying change in A1c and depression from baseline to 12-months.

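### The utilisation comparison adjusts for post-randomisation change in A1c and depression, and its composite has no scoring rule, so opposite effects on clinic and acute visits could offset.

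*Combined protocol and SAP*

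**What the plan says.** Self-reported healthcare utilisation is a secondary outcome (section 4, Design and Methodology, Measures). Section 5 (Data Analysis) sets out its analysis in two sentences.

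- The first creates one score: "Healthcare utilization outcomes both self-reported and obtained from LSCC will be harmonized into a composite score of utilization". It gives no list of components, no weights or signs, and no rule for when the two sources disagree.
- The second reads "Depending on the distribution of each aspect of utilization (ER visits, hospitalization, PCP visits), we will construct models to predict differences" between the arms, and these models are fitted "while covarying change in A1c and depression from baseline to 12-months".

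The table of measures in section 4 shows what each source covers. The self-report row is "Healthcare Utilization (PCP & BH clinic, Hosp, ED visits", collected at baseline and at 3, 6, 9 and 12 months. The record row is "Healthcare Utilization (PCP visits, BH visits", taken from "LSCC ElecHealthRecord" through data pulls during the program. It lists no emergency or hospital use and no baseline.

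In the intervention arm, "if the caller feels like the participant can benefit from checking in with their regular clinic provider, they may suggest doing so" (section 4, Overview). Controls are not given "the communications elements, telephone calls or letters, and otherwise continue with their normal standard of care".

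**The concern.** There are two linked problems.

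**Adjustment.** A1c is the primary outcome. Depression is the outcome on which the calling approach is said to have already worked (section 5). If the program changes utilisation, these are two routes by which it would do so. A model that holds them fixed asks what difference between arms remains among people with the same change in A1c and PHQ-9. That is not the effect of offering the program, and randomisation does not protect it.

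**Composite.** More contact with the clinic and fewer emergency or hospital visits could both be good results, yet they move a plain visit count in opposite directions. The background in section 2 cites a telephone program that reduced hospitalisation, and section 36 (Benefits to Society) says the study should help make the case for health systems to pay. A payer would read a fall in hospital use and a rise in clinic use quite differently, and a single undefined score may not show either.

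**Working it through.** **No figure to reproduce.** The documents give no rate, standard deviation, expected effect or power for utilisation. The power statement in section 5 concerns A1c, PHQ-9 and correlations only.

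**Step 1: what the adjusted coefficient estimates.** Let R be arm, M1 the change in A1c, M2 the change in PHQ-9 and Y utilisation. In linear form:

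- program effect on each change: M1 = … + a1·R and M2 = … + a2·R
- planned model: Y = … + c′·R + b1·M1 + b2·M2
- total effect: c = c′ + a1·b1 + a2·b2

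The planned model reports c′. It equals c only if a1·b1 + a2·b2 = 0. If the program lowers A1c and PHQ-9 (a1, a2 < 0) and smaller improvement goes with more acute use (b1, b2 > 0), both products are negative and c′ understates the fall in acute use. Count models do not split so neatly, but the same reasoning applies. No size can be given, because the documents supply none of these coefficients for utilisation.

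Even c′ is a valid direct effect only if no unmeasured factor drives both the changes and utilisation. Timing adds a difficulty. The 12-month change is fixed only at the end of the period over which visits are counted, so visits can themselves alter A1c and the covariate can be partly a consequence of the outcome.

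**Step 2: whether opposite effects could offset.** All rates here are assumptions, and an unweighted sum is one possible reading of the composite. Take control rates of 2.0 clinic and 0.40 acute visits per person, with acute use halved: 0.40 × 0.50 = 0.20 fewer.

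| Rise in clinic visits | Clinic change | Acute change | Change in sum |
|---|---|---|---|
| 0% | 0 | -0.20 | -0.20 |
| 5% | +0.10 | -0.20 | -0.10 |
| 10% | +0.20 | -0.20 | 0 |
| 15% | +0.30 | -0.20 | +0.10 |

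The sign reverses only above a 10% rise (0.20 / 2.0).

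**Step 3: sensitivity to the assumed rates.** Take 0.8 acute events per year cut by 30%: 0.8 × 0.30 = 0.24 fewer. The rise in clinic visits that fully offsets this is 0.24/3 = 8%, 0.24/4 = 6% or 0.24/6 = 4% for 3, 4 or 6 clinic visits per year.

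**Step 4: precision when clinic visits do not change.** Use 150 per arm, all followed, with variance = φ × mean and power = Φ(|d| / √((v0 + v1)/150) − 1.96).

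- Acute use alone, φ = 1: √((0.80 + 0.56)/150) = 0.0952; 0.24/0.0952 = 2.52; power 71%. With φ = 2, power is 43%.
- Sum with 4 clinic visits per year, φ = 1: √((4.80 + 4.56)/150) = 0.250; 0.24/0.250 = 0.96; power 16%.
- Over 3 to 6 clinic visits per year, power of the sum is 12% to 19% (φ = 1) or 8% to 12% (φ = 2).

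Under these assumptions the sum loses the acute signal through clinic-visit variation alone, without any opposing effect.

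**The case against.** **On the composite.** Harmonising two sources can mean reconciling overlapping reports, which is the opposite of counting them twice, and a signed or weighted score need not cancel. The sentence after the composite refers to the distribution of each aspect, which most naturally means a model per aspect. If emergency and hospital use are modelled on their own, a fall in them would be visible. Callers suggest clinic contact only at their discretion, the description of the calls in section 11 does not repeat the point, and nothing in the plan predicts more clinic visits.

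Most of this stands. A reader might infer that the plan adds the counts, counts primary-care and behavioural-health visits twice, or that benefits will cancel. The documents do not support any of these: no scoring rule is given, and cancellation needs an unsigned sum, a real rise in clinic visits and a real fall in acute use together. What remains is that the text does not say whether the models by aspect replace, feed or accompany the composite. Behavioural-health visits are collected but are missing from the aspects named in section 5.

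**On the adjustment.** The sponsor may want to know whether utilisation differs beyond what A1c and depression explain. That is a fair secondary question. It does not supply the total effect, and no utilisation comparison without these covariates is described.

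This is also one secondary outcome with no stated power. The primary A1c result does not depend on it.

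**Conclusion.** The adjustment is the firmer part. As written, the only described arm comparison of utilisation conditions on two post-randomisation outcomes that the program is meant to change. It therefore does not estimate the program's total effect and may be biased. If the program works through A1c and mood in the expected direction, a real reduction in acute use would be understated. The amount cannot be derived from the documents.

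The composite part holds as a gap in definition that carries a risk. Clinic visits and acute use are pooled with no scoring rule, their favourable directions may differ, and the two sources overlap only on primary-care and behavioural-health visits. Under an unweighted sum and the assumed rates in step 2, the result ranges from -0.20 to +0.10 visits per person according to the rise in clinic visits. That range shows what could happen and is not an estimate for this trial.

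The point should be settled before analysis. It bears on a secondary result that matters to the study's payer argument.

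**What to change.** 1. Remove change in A1c and change in depression from the utilisation arm comparison. Adjust only for baseline self-reported utilisation and the PHQ-9 randomisation stratum. The baseline should be self-report because no baseline is listed for the LSCC record. Any model containing A1c or depression change can stay as a labelled secondary analysis of mechanism.
2. In place of the composite, compare the arms on two separate outcomes: (a) emergency plus hospital visits, from self-report, the only listed source; and (b) primary-care and behavioural-health visits, from one source named in advance, with the other used as a check. In choosing the source for (b), note that section 4 names self-report as the secondary outcome.
3. Choose a count model suited to the distribution of each outcome, and state the follow-up window. Say explicitly that these two analyses replace the composite.

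The cost is a change of wording and one extra secondary model, so two secondary results are reported in place of one. Both data sources are already being collected, and neither the sample size nor the visit schedule changes.

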In this study we will use a randomized controlled trial to assess the impact of a 6-month long intervention of empathetic relationship building engagement with emotional and motivational support delivered telephonically for patients with diabetes at a Federally Qualified Health Center (FQHC). Telephone callers, lay people with light training on how to be empathetic and engaging in calls, will support participants' journeys on their own goals related to nutrition, exercise, sleep and medication adherence. They will not provide diabetes specific information, instead they will support people walking more, sleeping better, eating better and taking their medications. The impact of the program will be assessed primarily on Hemoglobin A1C levels and secondarily on depression and mental health at the end of the 6-month intervention, and in the following 6 months. Results will be compared to patients in the control arm that receive usual care. Participants will be recruited from our partner, an FQHC, Lone Star Circle of Care (LSCC) and include patients with Hemoglobin A1C of greater than 8.0 as measured at any point in the 12 months preceding enrollment.

- Chaoyang Li, Earl S. Ford, Tara W. Strine, Ali H. Mokdad. Prevalence of Depression Among U.S. Adults With Diabetes Diabetes Care Jan 2008, 31 (1) 105-107; DOI: 10.2337/dc07-1154
- Kahlon MK, Aksan N, Aubrey R, et al. Effect of Layperson-Delivered, Empathy-Focused Program of Telephone Calls on Loneliness, Depression, and Anxiety Among Adults During the COVID-19

Pandemic: A Randomized Clinical Trial. JAMA Psychiatry. 2021;78(6):616–622. doi:10.1001/jamapsychiatry.2021.0113

- Impact of a Telephonic Intervention to Improve Diabetes Control on Health Care Utilization and Cost for Adults in South Bronx, New York
- Bahman P. Tabaei, Renata E. Howland, Jeffrey S. Gonzalez, Shadi Chamany, Elizabeth A. Walker, Clyde B. Schechter, Winfred Y. Wu Impact of a Telephonic Intervention to Improve Diabetes Control on Health Care Utilization and Cost for Adults in South Bronx, New York. Diabetes Care Apr 2020, 43 (4) 743-750; DOI: 10.2337/dc19-0954

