#### To input text, click in the light grey area below.

Design: Randomized controlled trial.

**Population**: Adults with Hemoglobin A1C >8.0 measured at any point in the 12 months prior to enrollment, who have had at least one visit (Family medicine, behavioral health or other) with Lone Star Circle of Care within the past 12 months (in person or telehealth)

**Randomization:** Consented participants will be randomized to the intervention or control arm in a 1:1 ratio.

[figure not shown]
**Blinding:** Research staff involved in taking biomedical measurements will be blinded to participant status. Participants will complete surveys in person using a tablet or individual paper copy, thus research associates will remain blinded.

Time period: The study is divided into two parts.

- *Phase 1 (6 months)* is a randomized controlled trial testing the effect of telephone call-based empathetic engagement supported by caller-customized letters, together with small self-selected incentives (health tool) and caller-selected personal recognitions (small gifts selected based on the callers understanding of the participant), and low-literacy basic diabetes self-management information, against usual care. The primary outcome is Hemoglobin A1C (A1C) with repeated measures at baseline, 3 and 6 months.
- *Phase 2 (subsequent 6 months)* is the follow-up phase allowing us to *estimate* the 12 month longer term trajectory of A1C in Intervention and Control. To maximize the utility of the study to inform the most effective program design, participants in the control arm will receive the same opportunity to self-select health tool as the intervention arm received in Phase 1, but will make the choice during the 6

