For phase-II of the study, we have the opportunity to estimate two effects of interest including: a) the effect of the incentive and materials provision (2-selected items and health tool) on A1c among controls in phase-II over a period of 6-months compared to its effects when such provisions are coupled with empathy calls among intervention participants in phase-I (a between group effect estimate), b) the effects of exposure periods (phase-I and phase-II) on A1c and depression from baseline through 12-months separately for the two groups. In the case of the intervention group, the phase-I to phase-II difference gives clues to sustainability and in the case of the control group, the phase-I to phase-II difference provides a within-person estimate of the effect of incentive provision

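### Section 5 specifies no concurrent between-arm comparison of A1c or PHQ-9 after 6 months, although Section 2 says impact in months 7–12 will be compared with control

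*Combined protocol and SAP*

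**What the plan says.** Section 2 (Research Hypothesis) makes A1c the main measure of program impact, with depression and mental health in second place, and sets the timing and comparator as follows: "at the end of the 6-month intervention, and in the following 6 months. Results will be compared to patients in the control arm"; the sentence goes on to describe that arm as receiving usual care. Section 4 says Phase 2 allows the team to estimate the "12 month longer term trajectory of A1C in Intervention and Control". The measures table in Section 4 schedules A1c at "Baseline/3 mths/6 mths/9 mths/12mths" and PHQ-9 at the same five points, with no restriction by arm.

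Section 5 (Data Analysis) describes the A1c model thus: "We will test differences in the trajectory of A1c over the course of six-months with three assessments (baseline, 3- and 6-months". The group-by-time interaction in that model is the effect of interest. The PHQ-9 model is similar and uses three waves. For phase II, Section 5 lists two estimates:

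- (a) The effect of the incentives and materials on A1c among controls in phase II, set against intervention participants in phase I.
- (b) "the effects of exposure periods (phase-I and phase-II) on A1c and depression from baseline through 12-months separately for the two groups". For the intervention arm, "the phase-I to phase-II difference gives clues to sustainability".

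Treatment also changes at month 6. Under Sections 4 and 11, controls then receive the health tool, two gifts and the printed diabetes information. Intervention participants receive automated monthly texts in months 7–12.

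**The concern.** Whether the benefit lasts after the calls stop is one of the questions that the second six months can address, and Section 2 frames it as a comparison with control. The randomised arms are still under observation at 9 and 12 months, so the natural analysis is the arm difference at those visits. Section 5 does not ask for it. It looks instead at how the intervention arm's own course differs between phases.

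That within-arm quantity takes in anything that moves A1c or PHQ-9 over time in both arms. A real, lasting effect could look as if it had faded, or a fading effect as if it had lasted, because of changes unrelated to the program. The randomised evidence that would settle this is collected, but no analysis in the plan uses it for this purpose.

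**Working it through.** **Step 1. What each analysis in Section 5 covers.**

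| Analysis | Outcome | Arms compared over the same period? | Reaches 9 or 12 months? |
|---|---|---|---|
| Mixed model, group by time | A1c | Yes | No: baseline, 3 and 6 months |
| Mixed model, similar form | PHQ-9 | Yes | No: three waves, with A1c change from baseline to 6 months as covariate |
| Utilization models | Utilization | Yes | 12-month changes in A1c and depression enter as covariates, not as outcomes |
| Phase II (a) | A1c | No: controls in months 7–12, intervention in months 1–6 | Control arm only |
| Phase II (b) | A1c, depression | No: each arm on its own | Yes |

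No row gives a concurrent between-arm comparison of A1c or PHQ-9 after month 6.

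**Step 2. What the within-arm difference contains.** Let u(t) be the mean both arms would have under usual care at month t, P(t) the program effect relative to that, with P(0) = 0, and M the effect on controls at month 12 of the delayed materials. Then I(t) = u(t) + P(t) in the intervention arm. In the control arm C(6) = u(6) and C(12) = u(12) + M.

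- Within-arm change, month 6 to 12: I(12) − I(6) = [P(12) − P(6)] + [u(12) − u(6)]. The first bracket is persistence; the second is shared drift. One arm alone cannot separate them.
- Section 5 does not define the phase-I to phase-II difference. If it means a difference of six-month changes, it is [P(12) − 2P(6)] + [u(12) − 2u(6) + u(0)]. With no drift at all and the effect fully kept, P(12) = P(6), this equals −P(6), so zero does not mean sustained. It also takes in u(6) − u(0), where regression to the mean would appear for A1c, because Section 13(d) requires A1c of at least 7.5 at the baseline measurement.
- Between-arm differences: I(6) − C(6) = P(6), and I(12) − C(12) = P(12) − M. Shared drift and regression to the mean cancel. M does not cancel, and P(12) includes any effect of the monthly texts.

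**Step 3. The plan's own power figure.** Sections 5 and 15 give 150 per arm, three assessments, r = .30 and alpha .05, with f = .09 at 80% power and f = .10 at 90%. For a repeated-measures group-by-time F test, λ = f² × N × m / (1 − r), with df = (2 − 1)(3 − 1) = 2 and (300 − 2)(3 − 1) = 596.

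- f = .09: λ = 0.0081 × 300 × 3 / 0.70 = 10.41, power 83.0%.
- f = .10: λ = 0.01 × 300 × 3 / 0.70 = 12.86, power 90.3%.
- Smallest f: 0.0868 at 80% and 0.0995 at 90%, which round to the stated values.

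The figure reproduces, but it covers only the three-assessment, 6-month test. The plan gives no precision for months 7–12.

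**Step 4. Precision of a 12-month arm difference.** Baseline-adjusted SE in SD units = √[(2/n)(1 − r²)], with 1 − 0.30² = 0.91. The detectable difference at two-sided .05 and 80% power is (1.960 + 0.842) × SE = 2.802 × SE.

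- n = 150 per arm: SE = √(2/150 × 0.91) = 0.110; detectable 0.31 SD.
- n = 120 (20% loss, assumed): SE = √(2/120 × 0.91) = 0.123; detectable 0.35 SD.
- Range for assumed loss of 10% and 30% (n = 135 and 105): 0.33 and 0.37 SD.
- With no baseline adjustment and n = 150: 2.802 × √(2/150) = 0.32 SD, so a baseline correlation below .30 at month 12 would cost little.

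A formal test that the arm difference itself changed between months 6 and 12 is less precise: SE = √[(2/150) × 2(1 − 0.30)] = 0.137 SD; detectable 0.38 SD.

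The documents give no SD for A1c, so none of this can be turned into A1c points.

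**The case against.** The strongest reply is that the plan promises little here. The primary outcome is A1c at 6 months, Phase 2 is for estimation, and Section 5 claims only clues about sustainability. A reader might infer that the trial intends a firm statement that the benefit lasted or faded; the text does not say so. Moreover, Section 2 describes the comparator as usual care, which controls receive only until month 6, so no 12-month analysis could deliver that comparison literally. This stands as a limit on how the aim can be met. It does not remove the aim, because Section 2 extends the assessment into months 7–12 and Section 4 wants the trajectory in both arms.

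A reader might also infer that data after month 6 are used only within arms. That is too strong. Estimate (a) is a between-group use of the controls' phase-II A1c, and the utilization models compare arms with 12-month changes as covariates. Neither addresses durability: estimate (a) sets different periods against each other, covers A1c only and is about materials, and the utilization models do not treat A1c or depression as outcomes.

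Finally, the proposed contrast has its own bias. A control response to the materials shrinks the arm difference by M, which could be as large as the drift it removes. The monthly texts may push the other way. It is therefore wrong to call the 12-month difference a clean, or simply conservative, test of durability. This stands and governs how the result must be labelled. The contrast remains randomised and concurrent, which neither phase-II estimate is.

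**Conclusion.** The gap is real and should be closed. As written, Section 5 has no concurrent between-arm comparison of A1c or PHQ-9 after 6 months, and the only reading of sustainability is a within-arm difference that cannot separate persistence from shared drift or, for A1c, from regression to the mean. The 6-month primary comparison is unaffected.

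It would go too far to say that the trial's data cannot answer durability. They can inform it; the written analysis does not use them that way. Nor do the documents support putting a figure on how far the within-arm reading would mislead. They give no drift and no expected effect for this program. The 0.8-point reduction cited in Section 2 comes from a different program of 8 calls over 12 months, in people starting above 9%.

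The size that can be given is what the added contrast would detect with 80% power: about 0.31 SD with all 150 per arm, or 0.35 SD with an assumed 20% loss. This assumes that r = .30 holds to 12 months and ignores clustering by caller, although Section 11 gives panels of 10–25 participants and Section 5 intends to account for shared callers. It is a best case.

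**What to change.** In Section 5:

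1. Add the randomised between-arm differences in A1c and PHQ-9 at 9 and 12 months, from one model per outcome using all five waves in both arms. Keep the caller-clustering term.
2. Report them beside the 6-month arm difference, so that any change in the effect can be seen. A 12-month difference alone does not show fading.
3. Label the estimand as the full program followed by monthly texts versus usual care followed by delayed materials. State that a control response to the materials would shrink the contrast and that the texts may raise it. Align the usual-care wording in Section 2 for months 7–12.
4. Define the phase-I to phase-II difference. Keep the within-arm results as descriptive support and do not rest a sustainability conclusion on them alone.

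The cost is wording and one further model per outcome on data already scheduled, with no new visits or participants. The downside is a contrast against delayed materials rather than pure usual care.
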